#### **9.4.7.2 Safety Monitoring Committee**

The sponsor will establish a Safety Monitoring Committee (SMC) to evaluate AMI (including ST-segment elevation and non-ST-segment elevation) and AESIs (defined according to a pre-specified list of event terms including autoimmune, autoinflammatory, and hypersensitivity disorders provided in Appendix 4; other potentially immune-mediated medical conditions that do not appear in Appendix 4 are also considered AESIs).

All AMIs and AESIs occurring from immediately after the first study treatment on Day 1 through EOS Visit will be collected and evaluated.

Refer to SMC charter for details on the conduct, membership, and meeting frequency of the SMC.

#### **9.4.8 Serious Adverse Events**

All serious adverse events (SAEs), as defined in Section 10.3.1, will be evaluated from the time the consent is signed through EOS Visit. Any SAE must be reported to Dynavax or its designee within 24 hours of the knowledge of the event.

If the SAE is assessed as possibly or probably related to study treatment, it must be followed until it is considered stable or resolved, including beyond EOS Visit.

Any SAE assessed as not related to study treatment will be followed as clinically indicated until its resolution or, if nonresolving, until it is considered chronic or stable, or until study completion.

#### **9.4.9 Concomitant Medications**

Any prescription medication or over-the-counter drug taken by the subject from first study injection through Week 28 must be recorded in the eCRF. Use of vitamins and dietary supplements will not be collected unless they are indicated as a concomitant therapy for conditions directly related to undergoing hemodialysis. After Week 28, only prescription

medication or over-the-counter drug taken by the subject for the treatment of MAEs, SAEs, AMIs, or AESIs will be recorded on the eCRF through EOS Visit (further details regarding safety monitoring of AMIs and AESIs are provided in Section [9.4.7.2](#)).

## **9.5 End of Study**

An EOS Visit is required at Week 68 unless the subject is discontinued early from the entire study, in which case an Early Discontinuation Visit is required 28 days after the last dose.

## **9.6 Unscheduled Visit for Safety**

A UNS should be performed if there are suspected subject safety concerns. Procedures for the visit will depend on the reason for visit as determined by the treating principal investigator or sub-investigator. If a UNS is performed because of a safety concern related to study treatments, at a minimum, the following should be performed: a targeted physical examination based on subject-reported symptoms, serum chemistry, and hematology.

If the subject has permanent discontinuation of HEPLISAV-B (ie, discontinues treatment), the subject should continue to be followed for safety (as defined in Section 9.7) through EOS Visit. If the subject permanently discontinues the study, an EOS Visit (Section 9.5) should be scheduled 28 days after the date of last HEPLISAV-B administration.

## **9.7 Duration of Follow-up**

All subjects must be followed through EOS Visit (Section 10.0). If the subject is discontinued early from study treatment, the subject should not be withdrawn from the study and should continue to be followed for safety through EOS Visit. If the subject is discontinued early from the study, an Early Discontinuation Visit is required 28 days after the last dose.

# **10.0 REPORTING AND DOCUMENTATION OF MEDICALLY-ATTENDED ADVERSE EVENTS**

## **10.1 Post-Injection Reactions**

Local and systemic post-injection reactions are to be recorded on the subject diary. If they persist longer than 7 days (ie, 8 days or longer) and are medically attended (ie, subject seeks medical attention), they should also be recorded and reported as MAEs, per protocol Section [10.2](#). The severity of the post-injection reactions will be graded using the Toxicity Grading Scale for Healthy Adult and Adolescent Volunteers Enrolled in Preventive Vaccine Clinical Trials ([Appendix 3](#)).

Certain local and systemic events are routinely monitored in vaccine clinical trials as indicators of vaccine reactogenicity. It is recognized that each of these events, and particularly those of systemic nature, may under certain circumstances, in an individual subject, have a cause that is unrelated to study vaccine. However, as a matter of convenience and in accordance with common clinical practice, such events occurring within a specified period of time after immunization are herein termed ‘post-injection reactions’ and will be recorded as related to treatment.

Post-injection reactions documented by the subject via a diary will be collected, reviewed by the study nurse/coordinator with the subject, and recorded on the appropriate eCRF (Section [9.4.6](#)).

Further information is provided in the Study Reference Manual.

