## **8.0 MANAGEMENT OF STUDY TREATMENT TOXICITIES**

### **8.1 Reasons for Stopping a Subject From Receiving Additional Injections**

The investigator will discontinue study treatment and notify the sponsor if any of the following MAEs occur:

- Grade 4 post-injection reaction within 7 days after any study injection
- Clinically significant Grade 3 or higher systemic reaction (eg, angioedema, generalized urticaria) within 7 days after any study injection
- Grade 3 or 4 hypotension within 24 hours of any study injection
- Grade 3 or 4 respiratory reaction or symptoms occurring within 24 hours of any study injection
- Any life-threatening event, regardless of relationship to study drug
- Any AMI (further details regarding safety monitoring of AMIs are provided in Section [9.4.7.2](#))
- Any confirmed AESI (further details regarding safety monitoring of AESIs are provided in Section [9.4.7.2](#))

Subjects must also be discontinued from study treatment for any of the following reasons:

- Violation of protocol eligibility criteria
- Prohibited medications
- SAE assessed as a suspected adverse reaction (SAR) or adverse reaction (AR)
- Pregnancy or breastfeeding

Subjects may be discontinued from the study for any of the following reasons:

- Violation of protocol eligibility criteria (only if the subject has not received any study treatment)
- Prohibited medications (only if the subject has not received any study treatment)
- Noncompliance with study procedures as determined by the investigator or sponsor
- The discretion of the investigator

- The sponsor's administrative decision to terminate the study

The investigator or designee must notify Dynavax within 24 hours when a subject has been discontinued from treatment due to an MAE. The subject should not be withdrawn from the study and should continue to be followed for safety (as defined in Section 9.7) through EOS Visit.

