## **10.2 Adverse Events**

An AE is any untoward medical occurrence associated with the use of a drug, whether or not considered drug-related. An AE can therefore be any unfavorable and unintended sign (including a clinically significant abnormal laboratory finding), symptom, or disease temporally associated with the use of a medicinal (investigational) product, whether or not related to the study treatment. In this trial, only MAEs, AEs for which a subject seeks medical attention at a doctor’s office, clinic, study site, emergency room, or is hospitalized, will be collected.

Medical conditions present at Screening (ie, before informed consent is obtained) or present before the first study treatment (Day 1) are not MAEs and are not recorded on the MAE eCRF. These medical conditions should be adequately documented on the Medical History eCRFs. Any increase in severity or frequency of a medical condition documented as medical history after the first study treatment will be recorded as an MAE and will be captured on the MAE eCRF.

An uncomplicated pregnancy is not an MAE or SAE and should not be reported as an MAE/SAE. Subjects should be followed as described in Section [10.5](#).

The reporting period for all non-serious MAEs begins at the time of the first study treatment (Day 1) through EOS Visit. All MAEs will be captured on the MAE eCRF.

MAEs should be documented in terms of a single medical diagnosis. When this is not possible, the MAE should be documented in terms of signs and/or symptoms observed by the investigator or reported by the subject at each study visit.

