7.0 DEFINITIONS, COMPUTATIONS, AND CONVENTIONS

7.1 Definitions and Computations

Study Day

Study day will be calculated in reference to the date of first injection (Day 1). For visits conducted on or after the first injection date, study day is calculated as (visit date – first injection date + 1). For visits conducted before the first injection date, study day is calculated as (visit date – first injection date). There will be no Day 0.

Date of First Injection and Date of Last Injection of Study Vaccine

The date of the first injection of study vaccine is defined as the date a patient receives the first injection of the study vaccine. The date of the last injection of study vaccine is the date a patient receives the last injection of the study vaccine.

Treatment-Emergent Period

In this trial, only medically attended adverse events (MAEs), AEs for which a subject seeks medical attention at a doctor's office, clinic, study site, emergency room, or is hospitalized, will be collected.

The reporting period for all non-serious MAEs begins at the time of the first study injection (Day 1) through EOS Visit. All MAEs will be captured on the MAE eCRF.

Any SAE that occurs from the time the consent is signed through EOS Visit, whether or not the SAE is related to the study treatment, must be reported.

The treatment-emergent period is defined as time from the first study injection through EOS visit.

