9.7 Safety Analyses

Vaccine exposure and compliance will be summarized descriptively for safety population.

Safety data will be analyzed descriptively and will be based on the safety population. The most important safety parameters will be presented for all sites combined. Summary statistics will be used to describe the incidence of all post-injection reactions and MAEs (including SAEs, deaths, AMIs, and AESIs; further details regarding safety reporting of AMIs and AESIs are provided in Protocol Section 9.4.7.2). The incidence and proportion of post-

injection reactions and MAEs will be summarized. MAEs will be coded using the MedDRA SOC and PT.

The incidence of AMIs and major adverse cardiovascular events will be analyzed in subjects initiating hemodialysis after enrollment in the study and in subjects undergoing hemodialysis at the time of enrollment in the study.

The treatment-emergent period is defined in [Section 7.1](#).

Local and systemic post-injection reactions are to be recorded on the subject diary. If they persist longer than 7 days (i.e., 8 days or longer) and are medically attended (i.e., subject seeks medical attention), they should also be recorded and reported as MAEs, per protocol Section 10.2. The severity of the post-injection reactions will be graded using the Toxicity Grading Scale for Healthy Adult and Adolescent Volunteers Enrolled in Preventive Vaccine Clinical Trials.

Local reactions include redness, swelling and pain, and systemic reactions include malaise (not feeling well), headache, myalgia (body aches) and fatigue (feeling tired).

Post-injection reactions reported from day 1 to day 7 will be summarized by maximal severity and by vaccine group. The severity of local reactions, including redness and swelling will be categorized as none, 1 to ≤ 10 mm, >10 mm to ≤ 25 mm, >25 to ≤ 50 mm, >50 to ≤ 100 mm and >100 mm (severe local reactions).

The severity of pain and systemic reactions including malaise, headache, myalgia and fatigue occurring up to 7 days after each vaccination will be categorized as none, mild (no interference with activity), moderate (some interference with activity), severe (significant, prevents daily activity).

Temperature will be categorized as $<38^{\circ}\text{C}$ (no fever), $38\text{-}38.4^{\circ}\text{C}$, $38.5\text{-}38.9^{\circ}\text{C}$, $39\text{-}40^{\circ}\text{C}$ and $>40^{\circ}\text{C}$.

Each local and systemic reaction will also be categorized as none vs. any.

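### SAP 9.7's reaction categories do not match the Appendix 3 scale (no Grade 4 except fever), and no single rule says whether short, medically attended reactions count as MAEs

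*Protocol*

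**What the plan says.** **Severity of reactions.** SAP 9.7 states that reactions will be graded on the toxicity scale that the protocol reproduces as Appendix 3. It then lists its own summary categories. Pain and the systemic reactions run from none through mild and moderate to severe. Redness and swelling are in size bands ending above 100 mm. Temperature is in bands ending above 40 °C. Each reaction is also shown as none versus any.

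Protocol 8.1 opens its list with "The investigator will discontinue study treatment and notify the sponsor if any of the following MAEs occur", and the first item is "Grade 4 post-injection reaction within 7 days after any study injection".

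**Recording as an MAE.** Protocol 10.1 says diary reactions should also be recorded as MAEs under a two-part condition, "If they persist longer than 7 days (ie, 8 days or longer) and are medically attended (ie, subject seeks medical attention"), and refers the reader to 10.2. SAP 9.7 repeats it: "If they persist longer than 7 days (i.e., 8 days or longer) and are medically attended (i.e., subject seeks medical attention").

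Protocol 10.2 defines an MAE by where attention is sought: a doctor's office, "clinic, study site, emergency room, or is hospitalized, will be collected". SAP 7.1 carries the same definition: "In this trial, only medically attended adverse events (MAEs), AEs for which a subject seeks medical attention at" the same list of places. Neither definition has a duration test or an exception for solicited reactions. Both sections then say "All MAEs will be captured on the MAE eCRF".

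**Serious events.** Protocol 9.4.8 says "Any SAE must be reported to Dynavax or its designee within 24 hours of the knowledge of the event", and 10.3.2 puts every SAE on the MAE eCRF.

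**The concern.** The proportion of subjects with treatment-emergent MAEs is a primary endpoint (Protocol 4.2.1, SAP 4.0). The study has one arm and no hypothesis test (SAP 9.0), so the descriptive safety proportions are themselves the result.

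Two things could distort them. First, a programmer who follows the SAP 9.7 categories has no level in which to put a Grade 4 reaction other than fever, so the most severe reactions are merged with lower grades. Second, the two-part condition in 10.1 has no effect unless attended reactions of 7 days or less stay off the MAE form, whereas the 10.2 definition would put them on it. Two sites could treat the same event differently and each cite the protocol. Leaving such events out could only lower the MAE counts.

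The two gaps compound. A short attended reaction kept off the MAE form would be visible only in the reaction summary, which is where Grade 4 is missing.

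**Working it through.** The plan states no figure on this point, so the check sets the texts side by side and then bounds the size.

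**1. SAP 9.7 categories against Appendix 3**

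| Reaction | Highest level in SAP 9.7 | Appendix 3 | Can Grade 4 be shown? |
|---|---|---|---|
| Pain, headache, myalgia, fatigue | severe | Grade 4: ER visit or hospitalization | No |
| Redness | above 100 mm | Grade 4: necrosis or exfoliative dermatitis | No |
| Swelling | above 100 mm | Grade 4: necrosis | No |
| Malaise | severe | no Grade 3 or 4 exists | Severe has no counterpart |
| Temperature | above 40 °C | Grade 4: above 40 °C | Yes |

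Six reactions (4 + 1 + 1) have a Grade 4 that the summary cannot show. Necrosis within a reaction measuring 5.1 to 10 cm would fall in the band above 50 and up to 100 mm, which corresponds to Grade 2 by size.

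**2. A test case: headache, ER visit under 24 hours, resolved in 3 days**

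| Provision | Result |
|---|---|
| Appendix 3 | Grade 4, because of the ER visit |
| Protocol 10.2 and SAP 7.1 | MAE: attention was sought |
| Protocol 10.1 and SAP 9.7 | Condition not met: under 8 days |
| Protocol 8.1 | In the list headed as MAEs; sponsor notified |
| Protocol 10.3.2 | Not an SAE by hospitalization; another seriousness criterion could still apply |
| SAP 9.7 reaction summary | At most severe, and any |

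**3. Size**

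Inputs: N = 115 planned (Protocol 11.1, SAP 5.0), taken as the Safety Population; 4 injections per subject; SAP 9.7 counts each subject once.

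- Step per affected subject: 100/115 = 0.87 points at most, and zero on the any-MAE endpoint if that subject has another MAE.
- Exposure: 4 × 115 = 460 seven-day windows if every subject receives every injection. The plan expects 15% loss before Week 20, so 460 is an upper figure.
- The rate r of attended reactions of 7 days or less per injection is **an assumption**, as is independence between injections. Expected affected subjects = 115 × (1 − (1 − r)^4). Chance of at least one = 1 − (1 − r)^460. Fall in the any-MAE percentage if omitted = 100 × (1 − (1 − r)^4) × (1 − q), where q is the share of subjects with another MAE.

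| Assumed r | Expected subjects | Chance of at least one | Fall, q = 46% | Fall, q = 90% |
|---|---|---|---|---|
| 0.1% | 0.46 | 37% | 0.22 points | 0.04 points |
| 0.5% | 2.28 | 90% | 1.07 points | 0.20 points |
| 1% | 4.53 | 99% | 2.13 points | 0.39 points |

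The 46% is the MAE rate in label Study 3 (Appendix 2), a general adult trial, and is used only for illustration. The 90% is an assumption.

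For comparison, exact Clopper-Pearson 95% intervals are 36.8 to 55.6% at 53/115 and 83.5 to 95.1% at 104/115. The same method reproduces the plan's sample-size table (80/100: lower limit 70.8%, width 0.165).

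In a sparse table, such as related MAEs of Grade 3 or above, omitting two subjects would turn 2/115 (1.7%, interval 0.2 to 6.1%) into 0/115 (interval 0 to 3.2%). These counts are hypothetical. That table is more exposed because solicited reactions are recorded as related (Protocol 9.4.6), and a subject's unrelated MAEs do not mask the omission there.

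**The case against.** The strongest reply concerns recording. Section 10.1 is the specific rule for diary reactions and 10.2 the general definition. Taken literally, 10.2 collects nothing but MAEs, which would rule out the diary itself, so it can hardly govern that stream. The 7-day cut-off equals the diary period, and label Study 3 likewise reports unsolicited medically attended events. On this reading the plan has an ordinary solicited/unsolicited split, and the SAP merely carries over both rules. This is a fair reading and may be what was intended. It is not written down, however: 10.1 refers to 10.2, and 10.2 names its own exclusions (pre-existing conditions, uncomplicated pregnancy) without naming solicited reactions.

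Protocol 8.1 does not settle the matter the other way. It is a list of reasons for stopping injections, and its 7 days describe onset after injection, not duration.

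The Study Reference Manual, which the protocol cites for further detail on reactions, and the table shells are separate documents and were not available. Either might resolve part of this. They do not remove the mismatch in SAP 9.7's own text, which names a scale and then lists categories that cannot show it.

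A reader might also infer that serious or Grade 4 reactions would be lost altogether. The documents do not support that. SAEs must be reported and entered on the MAE eCRF, 8.1 requires sponsor notification of a Grade 4 reaction, and every reaction still appears as any. One loose end is that 10.3.1 words an SAE as a kind of MAE.

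**Conclusion.** Both parts hold, the first more firmly.

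1. As written, the SAP 9.7 categories cannot show Grade 4 for six solicited reactions, and they give malaise a level that Appendix 3 does not have. This rests on the text alone.
2. For non-serious attended reactions of 7 days or less, the documents do not say which rule decides the primary MAE count. The exclusion is implied by 10.1 and SAP 9.7, not stated. It would go too far to say that the plan instructs sites to leave these events out, or that the primary endpoint is materially biased.

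The effect on the any-MAE proportion is small: at most 0.87 points per affected subject, and about 2 points even at the highest assumed rate with q = 46%, against an exact interval about 19 points wide (55.6 − 36.8). The related and Grade 3+ tables are more sensitive. All rates are assumptions, because the documents give none. The point is worth correcting because the change is cheap and the safety result is purely descriptive.

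**What to change.** **Severity categories.** In SAP 9.7, add a Grade 4 level for pain, headache, myalgia, fatigue, redness and swelling. For redness and swelling it sits beside the size bands, since their Grade 4 is not a size. Match the malaise levels to Appendix 3.

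**Recording rule.** Reconcile Protocol 8.1, 10.1 and 10.2 with SAP 7.1 and 9.7 into one rule for the primary MAE endpoint. The preferred rule records a medically attended solicited reaction as an MAE whatever its duration, and keeps it in the diary summaries. The rule should state that diary review, the 30-minute observation and scheduled visits are not in themselves medical attention. Otherwise the reference to the study site in the 10.2 definition could draw routine reactogenicity into the endpoint.

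If the sponsor prefers the solicited/unsolicited split, 10.2 and SAP 7.1 should state the exclusion, and attended reactions of 7 days or less should be tabulated separately.

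**Cost.** Short wording changes in both documents, a few table categories and a memo to sites. Staff already review each diary with the subject. Under the preferred rule some events appear in both the reaction and MAE tables, and the MAE percentage may be slightly higher.

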## **10.2 Adverse Events**

An AE is any untoward medical occurrence associated with the use of a drug, whether or not considered drug-related. An AE can therefore be any unfavorable and unintended sign (including a clinically significant abnormal laboratory finding), symptom, or disease temporally associated with the use of a medicinal (investigational) product, whether or not related to the study treatment. In this trial, only MAEs, AEs for which a subject seeks medical attention at a doctor’s office, clinic, study site, emergency room, or is hospitalized, will be collected.

Medical conditions present at Screening (ie, before informed consent is obtained) or present before the first study treatment (Day 1) are not MAEs and are not recorded on the MAE eCRF. These medical conditions should be adequately documented on the Medical History eCRFs. Any increase in severity or frequency of a medical condition documented as medical history after the first study treatment will be recorded as an MAE and will be captured on the MAE eCRF.

An uncomplicated pregnancy is not an MAE or SAE and should not be reported as an MAE/SAE. Subjects should be followed as described in Section [10.5](#).

The reporting period for all non-serious MAEs begins at the time of the first study treatment (Day 1) through EOS Visit. All MAEs will be captured on the MAE eCRF.

MAEs should be documented in terms of a single medical diagnosis. When this is not possible, the MAE should be documented in terms of signs and/or symptoms observed by the investigator or reported by the subject at each study visit.

#### **10.2.1 Overdoses**

If an MAE is associated with or resulted from an overdose of HEPLISAV-B (for the purpose of this study defined as more than twice the protocol-specified dose), it will be documented on the MAE eCRF. If it is an SAE, it will also be reported to Dynavax or the Dynavax designee following the SAE reporting process (see Section 10.3.2).

